5.3. Safety Endpoints

Serum CRP, GPT levels and blood cell count at 24h, hemodynamic and febrile responses, as well as adverse events are considered safety endpoints.

We will specifically assess any signs of bleeding and perform a follow-up visit 1-2 weeks after the last study day.

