3.3.3 Timing

For this trial we chose to infuse 6.25mg/kg bodyweight over a period of two hours, which is the approved dose of this drug. The LPS bolus will be infused 1h after the start of the defibrotide infusion. We chose this dosing regimen based on the T_{max} of DF of two hours, the $T_{1/2}$ of 0.7 hours and the effects of LPS with a maximum approximately four hours after infusion of the bolus.

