5.1.7. Final Visit

The final safety visit will take place 7-14 days after the second trial period. A urinalysis, physical examination, blood sampling for safety parameters, ECG evaluation and documentation of all other relevant information including concomitant medication and adverse events, will be performed.

This visit will be the final visit of the trial and all subjects will be discharged from the trial thereafter unless a medical reason exists for another follow-up visit.

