5.4. Blood Sampling schedule, tubes and volume

Blood samples will be drawn at predefined time-points. Baseline measurements will be performed before infusion of any trial drug. Total blood volume will not exceed 240ml per period.

Table 1. Parameters, Samples and Schedule

Parameter	Sample	Time points
Coagulation biomarkers	Citrated plasma	Pre, 0h, 1h, 2h, 4h, 6h, 24h
Fibrinolysis biomarkers	Citrated plasma	Pre, 0h, 1h 2h, 4h, 6h, 24h
Endothelial biomarkers	EDTA-plasma/ Citrate plasma	Pre, 0h, 1h 2h, 4h, 6h, 24h
Inflammatory biomarkers	EDTA-plasma, Serum, Citrate-plasma	Pre, 0h, 1h 2h, 4h, 6h, 24h
FACS analysis	Citrated blood	Pre, 0h, 1h 2h, 4h, 6h, 24h

MPTF	Citrated plasma	Pre, -0h, 2h, 4h, 6h, 24h
Chemistry	Serum	Pre, 24h
Differential blood counts	EDTA	Pre, 0h, 1h 2h, 4h, 6h, 24h
Global coagulation assays	Citrate	Pre, 0h, 1h 4h, 24h
LPS quantification	Citrate	0h, 5min ,10min, 20min

Pre= Before Defibrotide/Placebo infusion and before LPS, 0h=Before LPS injection, other time-points relate to the LPS injection

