6.5. Potential inconveniences and risks for the subjects

6.5.1. Defibrotide

Defibrotide is approved by the FDA and the EMA for treatment of the sinusoidal obstruction syndrome (also called veno-occlusive disease) after hematopoietic stem cell transplantation or chemotherapy. Only few studies exist investigating the effects of DF in healthy volunteers^{7,37}. No serious or severe adverse events were reported in these trials.

The summary of product characteristics suggest that the most important adverse events of DF are hemorrhage, hypotension and coagulopathy²⁶. Of note, compared to a historical control group these side effects did not occur more frequently in the DF group indicating that these side effects may be due to the selection of patients, who were all thrombopenic critically ill patients³⁸.

No hypersensitivities or anaphylactic reaction were reported in the marketing trials^{20,38}. However, in previously marketed defibrotide products hypersensitivities and anaphylactic reactions have been reported²⁶. Thus, all participant will be made aware of that risk and special attention will be paid to potential anaphylactic reactions. We expect minor anti-coagulatory effects after infusion of DF. However, studies suggest that the effects of DF are only short termed and DF should be eliminated completely within 24 hours. All subjects will be made aware of an increased bleeding risk on the treatment days.

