6.5.5. Risk/benefit assessment

Endotoxin infusion in humans is a safe standard model, which induces a systemic inflammatory response and which has been safely used in more than 1000 volunteers at our institution. This inflammatory response is limited in duration and severity and can be used with restrictions as a model for the early phase of human sepsis.

Defibrotide has been used in clinical trials and clinical practice for over 30 years. Although many *in vitro* and animal studies have been published and effects in patients with SOS³⁸, with atherosclerosis obliterans³⁹ or peripheral arterial occlusive disease⁴⁰,

as a prophylaxis against deep venous thrombosis after surgery⁹, and other diseases have been investigated, the mode of action is still not entirely understood. However, in all those studies the use of DF was safe and no serious or severe AEs occurred.

The aim of this trial is to better define the pharmacodynamic effects of DF in a well established model of acute, transient inflammation in healthy volunteers. Furthermore, this trial will allow comparison of DF and other drugs that have already been investigated in this model and will help to generate further hypotheses about new indications of DF. The main risk of DF is a potential allergic reaction or bleeding episodes. However, the anti-coagulatory effects of DF will be closely monitored and strong anticoagulatory effects are not expected. Allergic reactions are rare, but must be considered a potential risk.

In conclusion we consider the benefits to clearly outweigh the risks in this study.

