6.6. Safety precautions

Throughout the trial-period the subjects will be observed by a physician. In addition, a physician with experience in emergency medicine will be at the unit during the first eight hours. The clinical trial center is equipped with monitoring facilities comparable to an intensive care unit.

The subjects will be supine with their chest tilted up throughout the trial period and their vital parameters monitored (ECG, heart rate and oxygen saturation continuously; blood pressure at 20 min intervals). Oral temperature will be checked every hour during the first 6 hours.

Frequent blood cell counts and monitoring of platelet function will be done.

Although our experience with more than 1000 LPS challenges showed no severe untoward effects, all adverse events will be managed by adequate medical measures according to standard practice. Evaluation of the safety parameters will be performed for each trial subject, which includes checks of C-reactive protein, GPT-levels blood cell count 24 hours after the endotoxin bolus.

7. Concomitant Illness and Medication

Concomitant illness: any illness that is present at the start of the trial

Concomitant medication: any medication other than the trial product that is taken during the trial, including screening and run-in periods

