11.3. Safety Analysis

All subjects who will receive trial drugs (including placebo) will be included in the safety analysis, which will compare the safety endpoints specified above between treatment periods. Tables of summary statistics will be presented. Detailed analysis specifications will be presented in a statistical analysis plan prior to analysis.

As LPS-infusion is associated with a number of adverse effects, particular interest will be focused on potential specific adverse effects of DF such as bleeding events or allergic reactions.

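### No clotting test is a safety endpoint, and the clotting assays drawn during defibrotide exposure belong to no endpoint, so a subclinical laboratory coagulopathy would not appear in the safety comparison

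*Combined protocol and SAP*

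**What the plan says.** Section 5.3 sets the safety endpoints: "Serum CRP, GPT levels and blood cell count at 24h, hemodynamic and febrile responses, as well as adverse events are considered safety endpoints". It adds a specific assessment of bleeding signs and a follow-up visit. Section 6.6 repeats the laboratory part, "which includes checks of C-reactive protein, GPT-levels blood cell count 24 hours after the endotoxin bolus". Section 11.3 will "compare the safety endpoints specified above between treatment periods", with particular interest in bleeding and allergic reactions, and leaves detailed specifications to a separate statistical analysis plan.

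On risk, Section 6.5.1 reports that "the most important adverse events of DF are hemorrhage, hypotension and coagulopathy" and expects minor anticoagulant effects that are short-lived, with the drug eliminated within 24 hours. Section 6.5.5 says that "the anti-coagulatory effects of DF will be closely monitored".

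On sampling, the global coagulation row of Table 1 (Section 5.4) reads "Pre, 0h, 1h 4h, 24h", with times counted from the LPS injection. Section 5.5.7 sends these assays to the hospital's central laboratory. They appear in neither the secondary endpoints (synopsis and 5.2.2) nor the safety endpoints (5.3).

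**The concern.** The safety of DF infusion in healthy volunteers is a stated objective. Of the three main risks in 6.5.1, hypotension is covered by the hemodynamic endpoint, and hemorrhage by bleeding signs and adverse events. Coagulopathy has no laboratory measure among the safety endpoints. The laboratory values that are listed are read when the drug has gone.

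The samples that could show a laboratory effect are scheduled, but no analysis section claims them. Followed as written, a report could describe the laboratory safety comparison as unremarkable without any clotting test having been part of it.

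**Working it through.** **1. DF exposure at each sampling time.** Inputs: half-life 0.7 h and LPS given 1 h after the start of DF (3.3.3); infusion over 2 h (6.1). On the LPS clock the infusion runs from -1 h to +1 h. One-compartment kinetics with constant input is an assumption.

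With t the hours since DF start:
- During infusion, the level is proportional to 1 - 2^(-t/0.7).
- After infusion, the level relative to peak is 2^(-(t-2)/0.7).

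| Time after LPS | t (h) | Level as % of end-of-infusion peak |
|---|---|---|
| 0h | 1 | (1 - 0.371)/(1 - 0.138) = 73% |
| 1h | 2 | 100% |
| 2h | 3 | 37% |
| 4h | 5 | 5.1% |
| 6h | 7 | 0.7% |
| 24h | 25 | 23/0.7 = 32.9 half-lives, about 1.3e-8% |

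This agrees with the plan's own statement that DF is eliminated within 24 hours. With an assumed half-life of 3 h, the 24h level would still be only 2^(-23/3) = 0.5% of peak. The final visit takes "A urinalysis, physical examination, blood sampling for safety parameters, ECG evaluation", but 7 to 14 days after period 2, so it is off drug too.

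**2. Which measurements reach a planned DF-versus-placebo comparison.**

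| Measurement | Drawn (Table 1) | Endpoint list | Comparison |
|---|---|---|---|
| Chemistry (taken to hold CRP, GPT) | Pre, 24h | 5.3 | 11.3 |
| Blood counts | Pre, 0h, 1h, 2h, 4h, 6h, 24h | 5.3 (24h only); 5.2.2 (differential counts) | 11.3 at 24h; 11.2.1 as secondary endpoint |
| F1+2, TAT, D-Dimer, t-PA, PAI-1 | Pre, 0h, 1h, 2h, 4h, 6h, 24h | 5.2.1, 5.2.2 | 11.2.1 |
| Thrombelastometry | no row of its own | 5.2.2 | 11.2.1 |
| Global coagulation assays | Pre, 0h, 1h, 4h, 24h | none | none |

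The last row amounts to 20 subjects x 2 periods x 5 times = 200 samples. Of these, 20 x 2 x 2 = 80 fall at 0h and 1h, 40 in DF periods and 40 in the matching placebo periods.

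**3. How much the adverse-event route can carry.** Event rates here are assumed, with 20 subjects and no placebo-period events.
- Chance of at least one DF-period event: 1 - 0.95^20 = 64% at a 5% rate; 1 - 0.90^20 = 88% at 10%.
- Two-sided exact McNemar test at 5%: five discordant subjects, all in the DF direction, give 2 x 0.5^5 = 0.063; six give 2 x 0.5^6 = 0.031. At least six are needed.
- Chance of six or more among 20: 1% at a 10% event rate, 20% at 20%, 58% at 30%.

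Overt events would probably be seen and described, but the formal comparison is weak.

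**4. What the scheduled assays could show.** A paired t comparison (two-sided 5%, 80% power) detects a mean difference of about 0.67 SD of the within-subject differences with 20 subjects, and 0.75 SD with the 16 LPS subjects. At 0h no subject has yet had LPS, so all 20 contribute to an LPS-free contrast of DF with placebo.

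**The case against.** The strongest reply is that the safety assessment is not blind to coagulopathy, and a reader might wrongly infer from the 24h rule that it is. Adverse events and bleeding signs are in 5.3 itself. Section 8.1.2 makes a laboratory abnormality an adverse event when it suggests disease or organ toxicity and needs active management, and 11.3 singles out bleeding. A marked clotting abnormality can enter by that route. This stands. What it leaves out is a prolongation below that threshold.

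A reader might also infer that an acute fall in platelets would be missed. The documents do not support that. Differential blood counts are a secondary endpoint drawn from Pre to 24h; 5.2.3 gives their purpose as assessing DF and LPS effects on cell counts, and 11.2.1 compares periods. For counts, the issue is only where the result is reported.

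On-drug coagulation biomarkers and thrombelastometry are compared as efficacy endpoints, so the promise of close monitoring is not empty. But they are not safety endpoints.

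The global coagulation row might be the thrombelastometry schedule: 5.2.3 calls thrombelastometry a global coagulation assay, and Table 1 has no separate row for it. Against this, 5.5.1 and 5.5.7 treat the two separately, and the screening list in 5.1.2 puts global coagulation assays beside blood counts and chemistry, which fits routine clotting tests. The ambiguity is real and itself needs settling.

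Finally, the trial is exploratory, the synopsis lists undefined safety parameters as a secondary variable, and a separate analysis plan, not among the documents, is to give detail. It may tabulate these assays. It does not change the endpoint list that the protocol sets, and where 6.6 spells out the safety parameters it names no clotting test.

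**Conclusion.** The point holds in a limited form and should be acted on. As written, the 11.3 comparison contains no clotting test, and its laboratory values are taken about 33 half-lives after the infusion ends. The assays at 0h, 1h and 4h are assigned to no comparison. A laboratory coagulopathy without bleeding or need for management would therefore be absent from the safety comparison, and a conclusion of laboratory safety would not extend to clotting.

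It does not follow that the trial is unable to reveal a DF coagulopathy, or that on-drug platelet changes go unexamined.

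The conclusion rests on reading global coagulation assays as routine central-laboratory tests distinct from thrombelastometry. The exposure figures assume one-compartment kinetics, but the finding that DF is gone by 24h is insensitive to that and agrees with 6.5.1. If the 0h sample is not drawn (the visit text in 5.1.3 and 5.1.5 lists baseline, 1, 2, 4, 6 and 24 hours only), 1h is the only post-baseline assay time within or at the end of the infusion.

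**What to change.** 1. In 5.3, name the routine clotting tests meant by global coagulation assays. State that they are separate from thrombelastometry, or give thrombelastometry its own row in Table 1.
2. Make those tests a safety endpoint, analysed as the within-subject DF-minus-placebo difference in change from Pre at 0h, 1h, 4h and 24h. Carry this into 11.3 and the separate analysis plan.
3. Reconcile the 0h draw in Table 1 with the visit text in 5.1.3 and 5.1.5.
4. Optionally, cross-reference the on-drug blood counts in the safety tables. CRP and GPT can stay at 24h.

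The cost is wording and one or two extra tables. Table 1 already schedules every sample, so no new samples, visits or subjects are needed.

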5.4. Blood Sampling schedule, tubes and volume

Blood samples will be drawn at predefined time-points. Baseline measurements will be performed before infusion of any trial drug. Total blood volume will not exceed 240ml per period.

Table 1. Parameters, Samples and Schedule

Parameter	Sample	Time points
Coagulation biomarkers	Citrated plasma	Pre, 0h, 1h, 2h, 4h, 6h, 24h
Fibrinolysis biomarkers	Citrated plasma	Pre, 0h, 1h 2h, 4h, 6h, 24h
Endothelial biomarkers	EDTA-plasma/ Citrate plasma	Pre, 0h, 1h 2h, 4h, 6h, 24h
Inflammatory biomarkers	EDTA-plasma, Serum, Citrate-plasma	Pre, 0h, 1h 2h, 4h, 6h, 24h
FACS analysis	Citrated blood	Pre, 0h, 1h 2h, 4h, 6h, 24h

MPTF	Citrated plasma	Pre, -0h, 2h, 4h, 6h, 24h
Chemistry	Serum	Pre, 24h
Differential blood counts	EDTA	Pre, 0h, 1h 2h, 4h, 6h, 24h
Global coagulation assays	Citrate	Pre, 0h, 1h 4h, 24h
LPS quantification	Citrate	0h, 5min ,10min, 20min

Pre= Before Defibrotide/Placebo infusion and before LPS, 0h=Before LPS injection, other time-points relate to the LPS injection

5.5. Preparations of samples

5.5.1. Thrombelastometry

Thrombelastometry (ROTEM; Pentapharm GmbH, Munich, Germany) will be performed using citrate anti-coagulated whole blood as previously described³³. In short, thrombelastometry measures the viscoelastic properties of whole blood during clot formation and clot lysis. Thrombelastometry is sensitive to infusion of 2ng/kg bodyweight LPS³³.

5.5.2. Coagulation specific and fibrinolytic parameters

F1+2, TAT, t-PA, PAI-1, D-Dimer and MPTF activity will all be detected in citrate anti-coagulated plasma samples. Whole blood samples will be centrifuged at 2000g for 15 minutes at 4 degrees Celsius and supernatant plasma will be transferred to aliquots of approximately 500µl each. These aliquots will be frozen and stored until batch analysis. MPTF will be centrifuged twice to generate platelet free plasma. F1+2, TAT, t-PA, PAI-1 and D-Dimer will be assessed by commercially available enzyme-linked immunoassays. MPTF activity will be assessed as previously demonstrated³².

5.5.3. Inflammatory biomarkers

EDTA-anticoagulated blood will be centrifuged at 2000g for 15 minutes at 4 degrees Celsius and supernatant plasma will be transferred to aliquots of approximately 500µl each. These aliquots will be frozen and stored until batch analysis. TNF-a will be measured by commercially available enzyme-linked immunoassays. We will assess changes in the proinflammatory exosome and the influence of DF on exosomes. Therefore, citrate anticoagulated blood will be centrifuged twice and isolated exosomes will be analyzed by mass spectrometry.

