11.2. Methods

Two-sided tests and a 5% critical value will be used throughout the trial. Test procedures to reduce multiple testing will be applied. Refer to the detailed, separate statistical analysis plan for further information.

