11.2.1 Efficacy Analysis

The efficacy analysis will compare changes in the primary and secondary efficacy endpoints described above between the placebo and the DF periods.

The repeated measures analysis of variance (ANOVA) will be used for analysis of treatment and period effects (treatment=independent factor, period=independent factor, outcome variable=dependent factor). When significant, post hoc comparisons will be performed with nonparametric tests for reasons of robustness: The Friedman ANOVA and the Wilcoxon test for post hoc comparisons will be used.

Furthermore, graphs showing the time profiles at the individual subject and group mean levels will be presented.

Multiple parameters will be tested. However, to reduce the number of tests a stepwise statistical analysis plan will be applied. Moreover, this study is of exploratory nature and correcting for multiple testing is therefore not necessary.

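### Exosomes are read out by mass spectrometry with no named analyte, summary or component count, and sections 11.2 and 11.2.1 conflict on multiplicity; component-wise 5% tests would flag about 5 of every 100 inert components

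*Combined protocol and SAP*

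**What the plan says.** **Endpoint.** Section 5.2.2 lists proinflammatory exosomes among the secondary endpoints (twice, once in the singular). Section 5.5.3 states the aim, "We will assess changes in the proinflammatory exosome and the influence of DF on exosomes", and the method, "isolated exosomes will be analyzed by mass spectrometry". Most of the other laboratory markers in sections 5.5.2 to 5.5.4 are immunoassays of a named analyte. For exosomes the text names no analyte, component list, summary score or number of components. Exosomes are described under inflammatory biomarkers, and that row of Table 1 in section 5.4 has seven sampling times. None is singled out for exosomes.

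**Testing.** Section 11.2.1 brings the secondary endpoints into the efficacy tests: "The efficacy analysis will compare changes in the primary and secondary efficacy endpoints described above between the placebo and the DF periods". Section 11.2 fixes the level: "Two-sided tests and a 5% critical value will be used throughout the trial".

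**Multiplicity.** Three statements bear on it:

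- Section 11.2: "Test procedures to reduce multiple testing will be applied". No procedure is named. The next sentence is "Refer to the detailed, separate statistical analysis plan for further information".
- Section 11.2.1: "to reduce the number of tests a stepwise statistical analysis plan will be applied". The steps are not given.
- Section 11.2.1, immediately after: "this study is of exploratory nature and correcting for multiple testing is therefore not necessary".

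No false discovery rule for exosomes appears in the supplied text.

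**The concern.** The exploratory argument is a common and tolerable one for a short list of pre-named markers that already have a known response to LPS. It is weaker for a readout that may return many quantities per sample. There, an uncorrected 5% rule can by itself produce a list of components that appear to change under defibrotide.

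Section 5.2.3 says that the effect of endotoxemia on exosome release has not been studied. So there is little earlier evidence against which a reader could sort true hits from chance ones. The trial also aims to generate hypotheses (synopsis and section 6.5.5), and a list of flagged components would be one of its products. At stake is which exosome components are declared affected by defibrotide.

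**Working it through.** **Inputs from the documents.** Two-sided level 0.05 (section 11.2); 16 subjects in the LPS group, each with a defibrotide and a placebo period, hence 16 pairs (sections 3.2 and 11.1). The plan states no false-positive rate and no number of tests for exosomes, so there is no figure of its own to reproduce. The 16 in section 11.1 was chosen for F1+2.

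**Assumptions.** The number of components, *m*, is not given. I take 100 to 1,000 as the working range and also show smaller values. I assume each component is tested on its own for defibrotide versus placebo, and that defibrotide has no effect. The correlation between components is not given, so I vary it from 0 to 0.8.

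**Expected false flags.** This is 0.05 × *m*, whatever the correlation:

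- *m* = 100: 0.05 × 100 = 5
- *m* = 500: 0.05 × 500 = 25
- *m* = 1,000: 0.05 × 1,000 = 50

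With the exact Wilcoxon signed-rank test on 16 pairs the attainable size is 0.0443, which gives 4.4 at *m* = 100 and 44 at *m* = 1,000.

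**Chance of at least one, independent components.** This is 1 − 0.95^*m*:

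- *m* = 1: 5%
- *m* = 10: 40%
- *m* = 20: 64%
- *m* = 59: 95%
- *m* = 100: 1 − 0.0059 = 99.4%

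**Chance of at least one, correlated components.** Simulated paired t-tests, 16 pairs, equal correlation *r* between all components, 2,000 replicates for *m* up to 100 and 600 above:

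| *m* | expected flags | *r* = 0 | *r* = 0.3 | *r* = 0.5 | *r* = 0.8 |
|---|---|---|---|---|---|
| 20 | 1 | 64% | 54% | 44% | 24% |
| 100 | 5 | 99% | 94% | 79% | 39% |
| 500 | 25 | 100% | 100% | 97% | 57% |
| 1,000 | 50 | 100% | 100% | 99.7% | 59% |

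A second run at *r* = 0.8 and *m* = 100 gave 41%, so about 40% is a fair figure. Strong correlation makes an empty list more common, but a list that does appear is longer. At *r* = 0.8 and *m* = 100 the simulated mean was 5.18 flags per trial, so given at least one it is 5.18 / 0.387 ≈ 13.

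**Does the ANOVA step change this?** Section 11.2.1 allows post hoc tests only after a significant repeated measures ANOVA. Run per component at 5%, that step itself passes about 5% of inert components. Multiplying 0.05 by 0.05 would be right only if the ANOVA and the post hoc test were independent, and both use the same subjects' data.

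**With control over the family.** With defibrotide inert and independent components, the chance of any listed component is:

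- Bonferroni: 1 − (1 − 0.05/*m*)^*m* = 4.9% for *m* from 100 to 1,000.
- Benjamini-Hochberg at 5% (4,000 replicates): 4.9%, 5.4% and 5.0% for *m* = 100, 500 and 1,000.

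The smallest two-sided exact Wilcoxon p-value with 16 pairs is 2/2^16 = 0.0000305. The strictest threshold, 0.05/*m*, can therefore be met up to 0.05/0.0000305, about 1,638 components.

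**The case against.** The strongest reply is that the text does not commit to what the arithmetic assumes. Mass spectrometry may be targeted at a few analytes, or its output may be reduced to one quantity. Section 5.2.3 speaks of exosome release, which could be a single amount, and a single summary carries the ordinary 5%. This stands. A reader might infer that a list of false components is guaranteed, but that needs a large component count, separate tests and weak correlation, and the documents give none of these.

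Second, section 11.2 does promise procedures and refers to a separate SAP, which may hold the answer. This also stands as a limit on what can be concluded. It does not settle the matter, because section 11.2.1 says expressly that correction is not needed. The two sections could be made to agree by reading the promised procedures as merely running fewer tests. That reading leaves each remaining test at an uncorrected 5%, which is the case worked above.

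Third, two further readings go beyond the text. One might infer that the stepwise plan only ranks endpoints and leaves tests within an endpoint free, but no steps are described. One might also infer that several sampling times multiply the false flags. With post hoc tests conditional on the ANOVA, that is not established.

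Fourth, the trial is openly exploratory and exosomes are one of more than a dozen secondary endpoints. That lowers the stakes without changing the error rate. Nor would the readout be worthless uncorrected: effect sizes, or a flag rate well above 5%, would still inform.

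**Conclusion.** The point holds as a conditional one. The supplied text leaves the exosome readout undefined, gives conflicting statements on multiplicity, and contains an express no-correction rule. If that rule is applied to many components singly, about 5 per 100 inert components are flagged per defibrotide-placebo contrast: 5 to 50 for an assumed 100 to 1,000. That expected count does not depend on correlation. The chance of at least one does: at 100 components it runs from about 99% (independent) through 79% (*r* = 0.5) to about 40% (*r* = 0.8). Neither the ANOVA step nor the undescribed stepwise plan can be shown to lower the rate.

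The result rests on the assumed component count and on component-wise testing, and the separate SAP could overturn it. It concerns one secondary endpoint and is a cheap improvement. The analysis of F1+2 is not affected.

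**What to change.** 1. Reconcile sections 11.2 and 11.2.1: name the procedures that section 11.2 promises, or withdraw the promise, and describe the steps of the stepwise plan.
2. In section 5.5.3 or the SAP, state what the mass spectrometry will quantify, which components form the family, and which time point or summary over time enters the test.
3. In section 11.2.1, exempt the exosome readout from the no-correction rule in one of two ways:
   - apply Benjamini-Hochberg at 5% across all exosome components, using each component's p-value for the defibrotide-versus-placebo treatment effect; or
   - pre-name one exosome summary at one time point as the endpoint, tested at 5%, and label all component results descriptive.

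Both suit a hypothesis-generating aim, and Benjamini-Hochberg is less strict than Bonferroni. The cost is SAP wording only, with no added subjects, samples or assays. The downside is fewer nominally significant components, including some that may be real.
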